3. STUDY DESIGN

3.1. Overall Design

This is a long-term, open-label, multicenter, study to evaluate the safety and efficacy of topical tapinarof cream, 1% in adults with plaque psoriasis. Subjects in this study completed treatment with tapinarof or vehicle in 1 of 2 pivotal Phase 3 pivotal efficacy and safety studies (Study DMVT-505-3001 or Study DMVT-505-3002). The study will consist of up to 40 weeks of treatment and a 4-week safety follow-up period.

At the completion of the Week-12 Visit of the pivotal study (Baseline [Day 1] in this study), eligibility of the subjects opting to enroll in this extension study will be confirmed. Study visits during the treatment period for all subjects will occur every 4 weeks (± 3 days). A Phone Call will be performed at Week 2 (Day 15). Unscheduled visits may occur, as needed. Subjects who withdraw from the study before Week 40 will return to the study center for an Early Termination Visit. The total duration of study participation will be approximately 44 weeks.

Subjects in the study will be treated as follows based on their PGA score from the Week 12 visit in the pivotal study (DMVT-505-3001 or DMVT-505-3002).

- Subjects entering with a PGA ≥ 1 will receive treatment with tapinarof cream, 1% until they achieve a PGA score of 0, at which time treatment will be discontinued and subjects monitored for durability of response. If/when disease worsening occurs, as evidenced by a PGA ≥ 2 , treatment will then be re-initiated and continued until a PGA of 0 is observed.
- Subjects entering with a PGA of 0 will have treatment discontinued and be monitored for durability of response. If/when disease worsening occurs, as evidenced by a PGA ≥ 2 , treatment will then be re-initiated and continued until a PGA of 0 is observed.
- This treatment and re-treatment pattern of use will be continued until the end of the study (ie, subjects may receive study treatment up until the Week 40 visit) (see Section 5.1.5.2).

Study drug will be dispensed, and subjects will be instructed on how to apply study drug. Subjects will apply the daily dose of study drug while at the site, under the supervision of site personnel, after efficacy and safety assessments have been completed.

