10.4.3. Safety Analyses

The number and percent of subjects with TEAEs will be summarized by system organ class and preferred term for all TEAEs, all TEAEs considered by the Investigator to be related to study drug, all SAEs, and all TEAEs leading to study drug discontinuation. All adverse event summaries will include information for adverse events that occurred after administration of the first dose of study drug until completion of the final study visit. Data listings will be provided for subjects who discontinued the study due to an adverse event and for subjects with an SAE.

Selected clinical laboratory data will be analyzed using descriptive summary statistics, including the number of nonmissing observations, mean and SD, median, upper and lower quartiles, minimum and maximum for values and changes from Baseline. Categorical safety data will be analyzed using frequency tables and, if applicable, shift tables.

Vital signs will be listed by subject and summarized by visit.

Mean scores from the LTS will be summarized by visit.

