3. STUDY DESIGN

This is a long-term, open-label, multicenter, study to evaluate the safety and efficacy of topical tapinarof cream, 1% in adults with plaque psoriasis. Subjects in this study completed treatment with tapinarof or vehicle in 1 of 2 pivotal Phase 3 efficacy and safety studies (Study DMVT-505-3001 or Study DMVT-505-3002). The study consists of up to 40 weeks of treatment and a 4-week safety follow-up period.

At the completion of the Week-12 Visit of the pivotal study (Visit 1, Baseline [Day 1] in this study), eligibility of the subjects opting to enroll in this extension study is confirmed. Study visits during the treatment period occur every 4 weeks (± 3 days). A Phone Call is performed at Week 2 (Day 15). Unscheduled visits occur, as needed. Subjects who withdraw from the study before Week 40 return to the study center for an Early Termination Visit. The total duration of study participation is approximately 44 weeks.

At the start of the study, subjects entering with a PGA ≥ 1 receive treatment with tapinarof cream, 1% until they achieve a PGA score of 0, at which time treatment is discontinued and subjects are monitored for durability of response. If/when disease worsening occurs, as evidenced by a PGA ≥ 2 , treatment will then be re-initiated and continued until a PGA of 0 is observed.

Subjects entering with a PGA of 0 will have treatment discontinued and they will be monitored for durability of response. If/when disease worsening occurs, as evidenced by a PGA ≥ 2 , treatment is re-initiated and continued until a PGA of 0 is observed.

The pattern of treatment, suspension and re-treatment is continued until the Week 40 visit.

Study drug dispensed to subjects during the clinic visits is applied once daily to all affected areas, including newly appearing lesions and lesions that improve during the study. Subjects

apply sufficient study drug to cover completely each lesion with a thin layer of study drug and record the time of study drug application in a daily diary provided by the study site. Subjects may treat fingernails, toenails, palms, soles, and scalp lesions with study drug; however, improvement of psoriasis is not assessed in these areas.

Safety assessments include AEs, local (application site) tolerability, clinical laboratory tests, vital signs, physical examinations, and investigator-assessed LTS. Efficacy assessments include a 5-point static PGA (0-4 scale), %BSA affected, the PASI, and subject-reported DLQI.

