6. SAMPLE SIZE DETERMINATION

The sample size of this study is based on the ICH E1 guideline on extent of population exposure to assess clinical safety for drugs intended for long-term treatment of non-life-threatening conditions. An estimated 850 subjects who complete Study DMVT-505-3001 or Study DMVT-505-3002 will be enrolled in this study at approximately 100 to 120 study sites in the US and Canada. A high discontinuation rate is anticipated in this long-term extension study. Approximately 300 subjects are expected to complete the study (40 weeks of treatment).

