11.11.1 Adverse Events

AE terms will be coded using Medical Dictionary for Regulatory Activities (MedDRA) dictionary. All AEs reported in current study are considered as treatment-emergent AE (TEAE) except for those AEs ongoing at the end of pivotal studies but resolved prior to the Visit 1 date in the extension study.

All TEAEs will be listed by subject, detailing the verbatim term given by the investigator, the preferred term (PT), system organ class (SOC), onset date and time, end date and time, ongoing at the end of pivotal studies (Y/N), duration (days), CTCAE grade, outcome, relationship to study drug, action taken with study drug, other action taken to treat the event, AE of special interest (Y/N), seriousness and criteria for seriousness.

AEs resolved prior to the Visit 1 date, Serious TEAEs (STEAEs), TEAEs leading to study discontinuation and TEAEs related to study drug will also be listed separately. The following adverse events of special interest (AESIs) will be identified and listed separately: contact dermatitis, folliculitis, and headache.

The number and percent of subjects with TEAEs will be summarized as incidence rates of:

- Any TEAE
- Any TEAE Excluding Those Ongoing at the end of the Pivotal Studies
- Any TEAE Ongoing at the end of the Pivotal Studies
- Any treatment-emergent AESIs
- Any treatment-emergent AESIs Excluding Those Ongoing at the end of the Pivotal Studies
- Any treatment-emergent AESIs Ongoing at the end of the Pivotal Studies
- Any treatment-related TEAE
- Any TEAE leading to study drug discontinuation
- Any TEAE leading to study discontinuation
- Any serious TEAE

- Death
- Treatment-related Serious TEAE
- Serious TEAE leading to study drug discontinuation
- Serious TEAE leading to study discontinuation
- TEAE (COVID-19)

Individual PTs will be summarized by SOC in alphabetical order and PT in descending order of frequency for the following subsets and subgroupings:

- All TEAEs
- All TEAEs by maximum CTCAE grade
- All TEAEs by maximum causality (not related, related) to the study drug
- All TEAEs Excluding Those Ongoing at the End of the Pivotal Studies
- All TEAEs ongoing at the end of the pivotal studies
- All treatment-related TEAEs
- All TEAEs leading to study discontinuation
- All TEAEs leading to study drug discontinuation
- All serious TEAEs

All TEAEs and all serious TEAEs will also be summarized by SOC (alphabetical order) and PT (descending order) for the following subgroups:

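### The adverse event tables in SAP 11.11.1 are crude percentages with no person-time and no split by drug status, so under stop-at-clear dosing and about 65% expected non-completion they estimate neither the on-treatment event rate nor the 40-week risk

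*SAP*

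**What the plan says.** **Dosing.** Treatment is intermittent by design. SAP Section 3 has subjects who enter with PGA ≥1 treated "until they achieve a PGA score of 0, at which time treatment is discontinued and subjects are monitored for durability of response"; drug restarts at PGA ≥2. For the others, "Subjects entering with a PGA of 0 will have treatment discontinued and they will be monitored for durability of response", so they are off drug from Day 1. Protocol 3.1 gives the same rule ("at which time treatment will be discontinued and subjects monitored for durability of response").

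**Attrition.** SAP Section 6 states: "An estimated 850 subjects who complete Study DMVT-505-3001 or Study DMVT-505-3002 will be enrolled in this study". About 300 are expected to complete. The same section warns: "A high discontinuation rate is anticipated in this long-term extension study".

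**Which events count.** Under SAP 11.11.1 every AE reported in this study is treatment-emergent, except events carried over from the pivotal studies that resolved before Visit 1. Drug status at onset plays no part. Protocol 10.4.3 is narrower and covers "adverse events that occurred after administration of the first dose of study drug until completion of the final study visit". The two definitions differ, but both include all off-drug time after the first dose.

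**How they are counted.** SAP 11.11.1: "The number and percent of subjects with TEAEs will be summarized as incidence rates of" the listed categories. Each subject counts once at each level, and SAP 11.11 takes all enrolled subjects as the population. SAP 11.4 derives days within treatment episodes for the exposure summaries, but SAP 11.11.1 does not use them.

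**Related outputs.** SAP 11.11.1 also plans a Kaplan-Meier figure of time to first event for contact dermatitis, folliculitis and headache, censored at study completion or discontinuation, and SOC/PT tables by four calendar periods of onset. The Local Tolerability Scale (LTS) is completed only if the subject was applying drug before the visit (Protocol 6.3.5 and Table 1, footnote i).

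**The concern.** Safety is the first objective, and a reader of the safety section will want two quantities: how often events occur while the cream is being used, and what share of subjects would have an event over 40 weeks. A crude percentage gives the second only if nearly everyone is followed for 40 weeks. It gives the first only if nearly all follow-up is on drug, or if the event is equally frequent on and off drug. The design secures none of these conditions. Calling the percentages incidence rates invites the reader to treat them as one of the two quantities.

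The study is open-label with no control arm, so a subject's own off-drug time is the only concurrent off-drug reference within it. It is an imperfect reference, but the AE tables in SAP 11.11.1 make no use of it.

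**Working it through.** **Inputs from the documents:** 850 enrolled and about 300 completing 40 weeks (SAP Section 6). The plan gives no dropout percentage, dropout timing, AE rates or share of time on drug. Everything below beyond the 64.7% is therefore illustration under stated assumptions.

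**Step 1. Non-completion.** 1 − 300/850 = 0.647, or about 65%. There is no separate planned figure to reproduce, because this comes from the plan's own two numbers.

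**Step 2. Follow-up to Week 40.** Assume a constant dropout hazard μ = −ln(300/850)/40 = 0.0260 per week. Mean follow-up = (1 − 300/850)/μ = 0.647/0.0260 = 24.9 of 40 weeks. Dropout uniform over 0–40 weeks gives 27.1. The extremes are 16.7 (all leave at Week 4) and 37.4 (all leave at Week 36).

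**Step 3. Crude percentage against true 40-week risk R.** Assume also a constant event hazard h = −ln(1 − R)/40, independent of dropout. Then

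crude = h/(h + μ) × [1 − exp(−40(h + μ))].

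- R = 10%: h = 0.00263; crude = 0.0919 × (1 − 0.9 × 0.353) = 0.063.
- R = 20%: h = 0.00558; crude = 0.1764 × (1 − 0.8 × 0.353) = 0.127.

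Other timings, using crude = 0.353 × R + 0.647 × (mean risk up to the dropout time):

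| True 40-week risk | Constant dropout | Uniform | All at Week 4 | All at Week 36 |
|---|---|---|---|---|
| 10% | 6.3% | 6.8% | 4.2% | 9.4% |
| 20% | 12.7% | 13.8% | 8.5% | 18.8% |
| 50% | 32.9% | 35.7% | 22.0% | 47.7% |

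**Step 4. Events that cluster early.** If onsets fall evenly over the first T weeks, with the constant dropout of Step 2, the share observed is (1 − exp(−μT))/(μT). For T = 4, 8 and 12 weeks this is 0.95, 0.90 and 0.86, so the understatement is about 5%, 10% and 14%.

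**Step 5. Pooling on- and off-drug time.** Let f be the share of follow-up on drug and q the off-drug rate divided by the on-drug rate. Pooled rate ÷ on-drug rate = f + (1 − f)q.

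- f = 0.5, q = 1/2: 0.5 + 0.25 = 0.75.
- f = 0.5, q = 0 (events only on drug): 0.50.
- q = 1 (event unrelated to drug): 1.00, whatever f is.

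Neither f nor q is given in the documents. The formula shows when pooling matters; it does not predict its size.

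**The case against.** The strongest reply is that pooling matches the target. Protocol 1.2 describes a drug for long-term intermittent use, and Protocol Section 10 speaks of repeated, intermittent courses. The percentage of subjects with an event under as-used dosing answers that question. This stands, and is why the crude tables should stay. It does not make them rates, and it does not remove the effect of dropout.

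Second, part of the gap is already covered. The Kaplan-Meier figures give a dropout-adjusted risk for headache, folliculitis and contact dermatitis if censoring is non-informative, and the LTS isolates on-drug local tolerability. Both points stand. But the figures censor at study exit, not at drug stop, so they still mix on- and off-drug time. Any TEAE, related TEAEs, serious TEAEs and other preferred terms have nothing similar. The onset-period tables run on calendar time with no at-risk denominator stated. The PGA status reported for events of special interest is not drug status: a subject at PGA 1 may be on or off drug.

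Third, an on/off comparison is confounded. Off-drug time starts at PGA 0 and re-treatment starts at PGA ≥2, so drug status follows disease status, and off-drug time selects subjects who cleared. This stands, and the comparison can only be descriptive.

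Two stronger readings are tempting. A reader might infer that the tables must make tapinarof look better tolerated. The documents do not show a net direction: pooling dilutes only events that are more frequent on drug, while carrying pivotal-study events into the TEAE count and imputing missing causality as related (SAP Section 8) push percentages up. A reader might also infer that the off-drug information is thrown away. It is not, because every TEAE is listed with its onset date and treatment-episode days are derived, so the analysis can be recovered.

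**Conclusion.** The point holds for the AE tables specified in SAP 11.11.1. They are percentages of enrolled subjects, mislabelled as incidence rates, and they estimate neither the on-treatment rate nor the 40-week risk.

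The size cannot be fixed from the documents. With a constant event hazard independent of dropout, a true 10% risk would show as 4.2% to 9.4% depending on when subjects leave, which is an understatement of between 6% and 58%. The 37% found under constant dropout is one case within that range, not an estimate for this trial. For events that cluster early the shortfall under constant dropout is about 5% to 14%. The effect of pooling depends on two unknowns and is nil for events equally frequent on and off drug.

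The text available to me ends at the heading of SAP Section 15, the outline of tables, so the absence of an exposure-adjusted or on/off-drug table rests on Section 11.11.1. This is a worthwhile, inexpensive addition for the safety objective. It does not make the planned counts wrong.

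**What to change.** In SAP 11.11.1:

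1. Keep the crude tables, but label them percentages of subjects.
2. Add exposure-adjusted incidence (first events per 100 patient-years) for any TEAE, related TEAEs, serious TEAEs, each event of special interest and frequent preferred terms, overall and by drug status at onset. State the denominator: time in the given status up to the first such event or study exit. Leave out events ongoing from the pivotal studies, which have no onset in this study.
3. Define on-drug time from the treatment-episode dates in SAP 11.7 together with dispensing and last-dose dates. Do not rely on diaries alone, because SAP 11.4 counts a missing diary as zero doses and would turn treated time into off-drug time. Exclude time after the last dose, because an episode ongoing at study end runs to the last PGA assessment, which can be the Week 44 visit. State how AE-driven interruptions are classified.
4. Add a sensitivity analysis that extends on-drug time by 4 weeks, the length of the protocol's own safety follow-up.
5. Present the on/off comparison as descriptive and say why.

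Optionally, extend the Kaplan-Meier method to any TEAE, which would give a 40-week risk without assuming a constant hazard.

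The cost is SAP wording, one derived variable and one or two tables, with no new data. The downside is that the attribution window is a choice; the sensitivity analysis shows how much it matters.

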1.2. Rationale for Study Design and Dose

As in the pivotal studies, this Phase 3 study continued to be conducted at multiple study centers in more than 1 country to enhance the possibility of inclusion of a wider range of population groups and to subsequently increase generalizability of the results. Tapinarof cream is intended for long-term, intermittent use in non-life-threatening inflammatory dermatologic conditions. Therefore, the 40-week duration of long-term, intermittent use of tapinarof in this study, in addition to the treatment received in the pivotal study, is expected to be an adequate duration to assess safety and efficacy of repeated treatment courses of tapinarof as recommended in the International Conference on Harmonisation E1 (ICH E1) guideline on the extent of population exposure to assess clinical safety for drugs intended for long-term treatment of non-life-threatening conditions [ICH, 1994], which recommends a minimum of 100 subjects be treated with the intended clinical dose and to be followed for AEs over at least 1 year.

The once daily topical application of tapinarof cream, 1% concentration administered in the pivotal studies will be continued in this open-label extension study.

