7.4. Follow-up Visit

Subjects will return to the study site 4 weeks (± 3 days) after last treatment to complete follow-up assessments as follows:

- Brief physical exam
- Vital signs measurements
- Urine pregnancy test (females of CBP)
- Blood sample collection for clinical laboratory tests (serum chemistry, hematology, diagnostic tests)
- Urinalysis
- Photography of a representative area of the subject's disease area (optional for subjects; at a subset of study centers)
- PGA score
- BSA affected calculation
- PASI
- DLQI
- AE recording
- Concomitant medication recording

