10. STATISTICAL CONSIDERATIONS AND DATA ANALYSES

This study is intended to show that tapinarof cream has a favorable safety and efficacy profile during repeated, intermittent treatment courses over an extended period of time.

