11.4 Study Medication Exposure and Compliance

Subjects will be characterized by a series of treatment episodes as defined in Section 11.7. These treatment episode definitions are based on attainment of specified PGA values.

The following exposure and compliance parameters will be summarized descriptively over the overall span of treatment episodes, overall and by DB treatment group:

- Total expected number of days exposed, calculated as the sum of number of days over all treatment episodes.
- Total number of doses administered within treatment episodes, calculated from the subject dose diary and summed over all treatment episodes. If a subject does not return diary or returns the diary with missing dosing record, the number of doses taken during that period is assumed to be 0.
- Grams (g) of study drug administered within treatment episodes, total will be summed over all treatment episodes. Drug administered is calculated as the summation of the difference between dispensed weight and returned weight for all returned tubes. Unreturned tubes will be assumed unused and will be included as 0 gram in amount drug used calculation. Average grams of study drug administered per expected day exposed and per doses administered will be calculated as the total grams / total number of days exposure (or total number of doses administered). Subjects with more than 1-day exposure but had no diaries returned will not have average grams per doses administered reported.
- Percent compliance will be calculated as the total number of doses administered within treatment episodes over the total expected number of days exposed.
- Subject compliance, defined as $\geq 80\%$ compliance over the entire duration of study. If the percentage of study medication compliance is unknown, the subject is assumed to be non-compliant with study medication.

In addition, the following exposure parameters will be summarized descriptively for the entire study (regardless of PGA status) overall and by DB treatment group:

- Total number of doses administered, calculated from the subject dose diary and in-clinic dosing. If a subject does not return diary or returns the diary with missing dosing record, the number of doses taken during that period is assumed to be 0.

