11.7 Efficacy Endpoints

Efficacy endpoints are as follows:

For subjects entering the study with a PGA score of clear (0):

- Proportion of subjects who experience PGA ≥ 2 at least 1 time during the study.
- Proportion of subjects who never experience PGA ≥ 2 throughout the study.
- Time to first worsening (PGA ≥ 2), defined as days from date of Visit 1 date to the date of first occurrence of PGA ≥ 2 . Subjects who never experience PGA ≥ 2 throughout the study will be censored at the date of their last PGA assessment.

For subjects entering the study with a PGA score ≥ 1 :

- Proportions of subjects who achieve PGA = 0 at least 1 time during the study

• [REDACTED]

• [REDACTED]

[REDACTED]

For subjects entering the study with a PGA score ≥ 2 :

- Proportions of subjects who achieved PGA = 0 or 1 at least 1 time during the study.
- Proportions of subjects who never achieve PGA = 0 or 1 throughout the study.

The following endpoints will be summarized over subjects in ITT population:

- Duration (days) of treatment episodes, defined as time (days) from the date of each PGA ≥ 2 (or PGA ≥ 1 for the first episode) to 1 day before each subsequent treatment success (PGA = 0). The date of the last PGA assessment will be used as the end date for episodes ongoing at the end of the study.

- [REDACTED]
- [REDACTED] \geq [REDACTED]
- [REDACTED]
- [REDACTED]
- [REDACTED]
- [REDACTED] change and percent change from baseline in %BSA affected by visit (OC and LOCF).
- [REDACTED] change and percent change from baseline in PASI score by visit (OC and LOCF)
- [REDACTED] \geq [REDACTED]
- [REDACTED] \geq [REDACTED]
- [REDACTED] \geq [REDACTED]

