11.11 Safety Analysis

All safety parameters will be summarized over the ITT population of all enrolled subjects, overall and by DB treatment group.

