- Age (<65 and \geq 65 years old)
- Sex
- Race (White, Other)

Furthermore, TEAEs will be categorized by day of onset among the following 4 categories:

- \leq 12 weeks
- >12 to \leq 24 weeks
- >24 to \leq 40 weeks
- >40 weeks.

For each of these categories, TEAEs will be summarized by SOC in alphabetical order and PT in descending order of frequency. TEAEs ongoing at the end of the pivotal studies will be considered in the first category (i.e. day of onset \leq 12 weeks).

At each level of summarization, a subject will be counted once if he/she reported one or more events. The severity of TEAEs and relationship to study drug will be summarized in a similar

manner. For summaries of relationship to study drug, a subject will be classified according to the closest relationship. For summaries of TEAE CTCAE grade, a subject will be classified according to the worst grade.

For AESIs, summarization will be more extensive, reflecting the more detailed information collected. Information summarized will include number of events per subject, earliest onset day, duration (in days), causality, grade and seriousness of AESIs, outcome, actions taken, assorted physical characteristics of the AESIs, and demographic/baseline characteristics and PGA status of the subjects experiencing them. Each type of AESI will be summarized separately. If a subject has more than one treatment-emergent occurrence of an AESI, the subject's maximum duration, highest levels of causality and seriousness, maximum grade and generally the most extreme level of each characteristic will be summarized. If an AESI was ongoing at end of study (EOS), it will not be included in the duration summary. AESIs ongoing at the end of pivotal studies will also be included in the summary.

A Kaplan-Meier figure will be generated for each AESI of time to first event for events starting during the study. Subjects not experiencing the AESI will be censored at the date of study completion or discontinuation. AESIs ongoing at the end of pivotal studies will not be included.

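### No readable SAP adverse event or AESI summary separates first-course, re-treatment and drug-free time, although the study is meant to show safety over repeated, intermittent courses

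*SAP*

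**What the plan says.** Protocol Section 10 states the purpose as a "favorable safety and efficacy profile during repeated, intermittent treatment courses over an extended period of time". Protocol Section 1.2 says the 40 weeks, added to the pivotal-study treatment, "is expected to be an adequate duration to assess safety and efficacy of repeated treatment courses of tapinarof". Under Protocol Section 3.1, drug stops at PGA 0 and restarts at PGA 2 or more, until Week 40. Subjects who enter clear start off drug.

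SAP 11.11 states: "All safety parameters will be summarized over the ITT population of all enrolled subjects, overall and by DB treatment group". SAP 11.11.1 treats every AE reported in the extension as treatment-emergent, except pivotal-study events resolved before Visit 1. It then says: "Furthermore, TEAEs will be categorized by day of onset among the following 4 categories". The windows are up to 12, >12 to 24, >24 to 40, and >40 weeks. SAP 10.3 counts study day from Visit 1, not from the start of a course. Each AESI also gets a Kaplan-Meier figure of time to first event.

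The SAP does define treatment episodes, but uses them for exposure, compliance and efficacy. SAP 11.4 has "Total expected number of days exposed, calculated as the sum of number of days over all treatment episodes". SAP 11.7 adds: "The date of the last PGA assessment will be used as the end date for episodes ongoing at the end of the study".

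**The concern.** The stop-and-restart rule puts up to three states into each subject's follow-up: a first course, drug-free intervals and re-treatment. The safety summaries arrange events by calendar time in the study, and that does not identify the state. If contact dermatitis or folliculitis (both AESIs under Protocol 8.1.3) were more or less frequent on re-exposure, the planned tables and curves would show it only after dilution. An AESI rate that rises, falls or stays flat over the middle windows could come from a changing mix of states as easily as from a changing risk on drug.

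**Working it through.** **1. What each planned summary separates**

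| SAP item | Split by | What remains pooled |
|---|---|---|
| TEAE tables (11.11.1) | DB group, age, sex, race, grade, causality | all three states |
| Onset windows (11.11.1) | study day | all three states in the two middle windows; >40 weeks is essentially drug-free |
| AESI Kaplan-Meier (11.11.1) | time from Visit 1 | all three states |
| AESI PGA status (11.11.1) | undefined; only subjects with the event | no rate; PGA 1 can be on or off drug |
| Relatedness tables (11.11.1) | investigator causality | course number |
| LTS (11.11.2) | visit, DB group | first course and re-treatment (in effect on-drug only, Table 1 footnote i) |

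**2. Hand calculation (illustration)**

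Take the fastest cycle the 4-weekly visits allow: 4 weeks on, 4 weeks off. With first-course event rate h, re-treatment rate Rh and off-drug rate ch, the rate in a window is h × (f1 + R·f2 + c·f0). Here f1, f2 and f0 are the shares of time in first course, re-treatment and off drug.

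- Entry at PGA 1 or more. Weeks 0-12 hold 4 first, 4 off and 4 re-treatment; weeks 24-40 hold 8 off and 8 re-treatment. With c = 0:
  - R = 3: early (4 + 12)/12 = 1.33; late 24/16 = 1.50; ratio 1.13.
  - R = 1: early 8/12 = 0.67; late 8/16 = 0.50; ratio 0.75.
- Entry at PGA 0. Weeks 0-12 hold 8 off and 4 first; weeks 24-40 hold 8 and 8. With c = 0 and R = 1: early 4/12 = 0.33; late 0.50; ratio 1.50.

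So a threefold increase can read 1.13 in one entry group, while no increase reads 1.50 in the other.

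**3. Simulation**

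From the documents: 850 enrolled, about 300 completing, 40 weeks, visits every 4 weeks. Assumed: first-course AESI hazard 0.005 per week; 10% entering clear; median 12, 20 or 30 weeks to clear; median 4, 8, 16 or 24 weeks to relapse; off-drug hazard 0, half or equal to the first-course hazard.

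- Weeks 0-12 are 74-84% first course and 1-5% re-treatment.
- Weeks 24-40 are 17-46% first course, 17-54% re-treatment and 15-62% drug-free.
- First-AESI rate ratio, weeks 24-40 to weeks 0-12:

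| Median weeks to relapse | True threefold re-treatment hazard |
|---|---|
| 4 | 1.58-1.89 |
| 8 | 1.44-1.68 |
| 16 | 1.21-1.48 |
| 24 | 0.96-1.36 |

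With no increase, the ratio is 0.50-1.03 over all settings. In single trials of 850 with a threefold hazard (12 weeks to clear, no off-drug events), the ratio is at or below 1 in under 1% of trials at 4 weeks to relapse, 24% at 16 weeks and 54% at 24 weeks.

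**4. Rate by course**

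Re-treatment events per on-drug week, divided by first-course events per on-drug week, returns 2.9-3.1 for a true 3 and 0.97-1.04 for a true 1. This assumes one first-course hazard for everyone.

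**5. Why DB group is needed**

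Enrollees had received tapinarof or vehicle (Protocol 3.1). Let v be the share of first-row time that is newly exposed at k times the base hazard. A true ratio R then reads R/(1 + v(k − 1)). With v = 1/3 throughout and R = 1, this is 0.75 for k = 2 and 0.60 for k = 3. Simulations that confine the higher hazard (assumed 2-3 times) to early exposure give 0.61-0.89 across assumed ex-vehicle shares. The ex-tapinarof group alone returns 1.0.

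**6. Why SAP 11.7 episode days will not serve unchanged**

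An ongoing episode ends at the last PGA. That can be the follow-up visit, which falls 4 weeks (±3 days) "after last treatment to complete follow-up assessments as follows" and includes a PGA (Protocol 7.4). In the simulation, 11-15% of re-treatment episode time and 1-3% of first-course time is then drug-free. At the midpoints, a true 1.0 reads (1 − 0.13)/(1 − 0.02) = 0.89. The simulated range is 0.87-0.90, assuming no off-drug events and that all completers attend Week 44.

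**7. Precision in one trial of 850 (12 weeks to clear)**

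| True ratio | 4 weeks to relapse | 24 weeks to relapse |
|---|---|---|
| 1 | 0.60-1.57 | 0.47-1.78 |
| 1.5 | 1.00-2.24 | 0.73-2.47 |
| 3 | 2.15-4.29 | 1.84-4.57 |

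These are 2.5th to 97.5th percentiles of the by-course ratio.

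**The case against.** The safety endpoints in Protocol Section 2 ask for the incidence, frequency and nature of events. Pooled summaries over everyone on the stop-and-restart regimen deliver that. The purpose statements concern safety under the regimen and do not pose a comparison between courses. This stands: the plan meets its listed endpoints, and the gap is against the stated purpose only.

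The causality tables also help. Protocol 8.2.2 bases relatedness on temporal plausibility and response to withdrawal or rechallenge, so related events are partly cleared of drug-free noise. This stands in part, because those tables give no course number. By-subject listings would allow a later derivation, but nothing commits to one.

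A threefold effect is assumed, and nothing in the documents predicts it. Protocol 1.3.1.1 reports no evidence of sensitization in nonclinical studies. Re-treatment also comes later and in selected subjects; a study-time trend alone can give a by-course ratio of 1.41-1.47. Both points stand and limit the table to description.

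A reader might infer that every onset window mixes all three states. That goes too far: the last is essentially drug-free, and the first is mostly first course in the assumed settings.

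**Conclusion.** The point holds as an optional improvement. No readable AE or AESI summary separates first-course, re-treatment and drug-free time, and the >12 to 24 and >24 to 40 week windows and the AESI curves cannot stand in for that split.

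The dilution is moderate when relapse is quick (a true 3 reads 1.58-1.89) and strong when it is slow (0.96-1.36, against 0.50-1.03 with no increase). These sizes rest on assumed hazards and assumed clearing and relapse times.

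A reader might infer that the safety analysis is wrong, that a re-treatment risk is suspected, or that the SAP certainly lacks such a table. The documents support none of these. The endpoints are met, no increase is predicted, and SAP Section 15 has no readable content, so a by-course table there cannot be excluded.

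**What to change.** In SAP 11.11.1 add one descriptive table for each AESI and for treatment-related TEAEs.

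- **Rows:** first course in this study, re-treatment, drug-free interval. Label the first row *continued treatment* for ex-tapinarof subjects and *first exposure* for ex-vehicle subjects. Count the first worsening of an ex-tapinarof subject who entered at PGA 0 as re-treatment.
- **Columns:** by DB treatment group (mandatory) and overall. Give subjects at risk, subjects with an event, events, and events per 100 subject-weeks.
- **On-drug time:** from the start of each course to the earliest of the PGA 0 visit, last dose or permanent discontinuation, and the Week 40 visit, less recorded interruptions. Do not use the 11.7 episode end dates unchanged.
- **Events:** exclude those ongoing from the pivotal studies, as the AESI Kaplan-Meier figure already does. Flag events whose onset day was imputed under SAP Section 8, since imputing the first of the month can assign the wrong state.

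LTS by course is optional.

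The cost is a new derivation of course number and on-drug dates from data already collected. Counts will be small. In the simulations 126-437 of 850 subjects start re-treatment, with 8-30 re-treatment events per AESI if there is no increase and 24-90 at threefold; the DB groups will have fewer. The table should state that it is descriptive and cannot reliably detect a 1.5-fold increase.
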